3.8.2 Laboratory Assessments

Laboratory assessments of Complete Metabolic Panel (CMP) and Complete Blood Count (CBC) as well as urine pregnancy tests for women of childbearing potential will be performed at the local clinical laboratory of the clinical site. CMP and CBC will be collected at screening, Day 1 and Day 28. Summaries of baseline assessment and change from baseline for laboratory assessments will be summarized by number of subjects, mean, standard deviation, median, minimum and maximum and by cohort, relative autograft mesh ratio group at the SOMA Tx site (m+1 and m+2), and for all subjects.

CMP and CBC laboratory results will be classified as status of 'Low', 'Normal' and 'High' as defined at the local clinical laboratory of the clinical site. Shift tables summarizing status of changes from baseline at Day 28 according to baseline status will be provided for subjects with both baseline and Day 28 results by cohort, relative autograft mesh ratio group at the SOMA Tx site (m+1 and m+2), and for all subjects.

CMP and CBC parameters will be categorized as normal, non-clinical significance and clinical significance at Baseline and Day 28 by the clinician. Shift tables of change from baseline to Day 28 will be created for laboratory results using clinical significance categories by cohort, relative autograft mesh ratio group at the SOMA Tx site (m+1 and m+2), and for all subjects.

3.8.3 Vital Signs

Subjects vital sign data was collected at each visit and the visit for confirmation of healing (closure). The averages value and change from baseline in vital signs of body temperature, systolic blood pressure (SBP), diastolic blood pressure (DBP), heart rate (HR), and respiratory rate, will be summarized by number of subjects, mean, standard deviation, median, minimum and maximum, and by cohort, relative autograft mesh ratio group at the SOMA Tx site (m+1 and m+2), and for all subjects.

3.8.4 Immunologic Responses to StrataGraft: Panel Reactive Antibodies (PRA) and Anti-Bovine Serum Albumin (anti-BSA) Antibody

Blood samples will be collected prior to placement of StrataGraft and again at Month 3 to assess changes in Panel Reactive Antibodies (PRA) and anti-Bovine Serum Albumin (anti-BSA) levels. PRA is a measure of antibody formation to non-self human proteins such as those found in StrataGraft. The cells in StrataGraft are cultured in media containing BSA and anti-BSA antibodies may be formed with exposure to StrataGraft.

PRA and anti-BSA antibody (IgG) assessments will be performed by a central laboratory. PRA will be screened and tested for HLA class I and II allelic reactivity at Day 1 (baseline) and Month 3. The number and percentage of subjects that are HLA class I and II positive will be provided for Baseline (Day 1) and for Month 3 by cohort, relative autograft mesh ratio group at the SOMA Tx site (m+1 and m+2), and for all subjects.

Additionally, the number and percentage of subjects that are HLA allele positive will be provided for each visit and for each allele by cohort, relative autograft mesh ratio group at the SOMA Tx site (m+1 and m+2), and for all subjects.

PRA parameters and anti-BSA IgG will be categorized as normal, of non-clinical significance, and of clinical significance at Baseline and Month 3 by the central laboratory. Shift tables indicating changes from Baseline to Month 3 for PRA results will be created using clinically significant categories by cohort, relative autograft mesh ratio group at the SOMA Tx site (m+1 and m+2), and for all subjects.

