3.3. Benefit/Risk Assessment

Results to date indicate that StrataGraft is well tolerated and no clinically observable allogeneic immune responses have been reported. The most common noted adverse reaction associated with StrataGraft treatment is pruritus.

Theoretical risks specific to StrataGraft treatment include development of an immune response to the allogeneic cells of StrataGraft and the need for subsequent autografting of the StrataGraft treatment site. Because StrataGraft contains human cells, there is the possibility of transmission of an infectious agent. Additionally, StrataGraft contains glycerin, therefore in patients who have a glycerin sensitivity, there is a risk of an allergic reaction.

While no clinically relevant immune response to StrataGraft has been seen in STRATA2001, STRATA2011, STRATA2014, or STRATA2016, or there is a theoretical possibility that subjects who mount an immune response to the allogeneic cells of StrataGraft and who then become candidates for receiving solid organ transplants could experience a narrowing of the suitable donor pool.

Data from STRATA2001 showed that autograft take after treatment of the wound bed with StrataGraft was similar to cadaver allograft, 97% and 96%, respectively. Additionally, the 2 STRATA2011, the 3 STRATA2014, and the 3 STRATA2016 subjects who received autograft at

sites previously treated with StrataGraft showed complete wound closure before or at Month 3, demonstrating that treatment with StrataGraft does not impede achievement of wound closure in the event autograft is used to achieve definitive closure.

StrataGraft is a xenotransplantation product because in the past, one of the cell types used to make StrataGraft was grown with mouse cells. The cell banks have been tested and found to be free of detectable infectious agents and mouse cells are no longer used in the manufacture of StrataGraft. There have been no identified health concerns associated with these mouse cells.

Recipients of xenotransplantation products are generally not eligible, per federal regulations, to donate whole blood, blood components, source plasma or source leukocytes. However, individual blood banks may request an exception from FDA. StrataGraft recipients wishing to donate blood or blood products should check with their donation center. StrataGraft recipients who otherwise meet the donor requirements are eligible to donate human cells, tissues, breast milk, ova, sperm, or body parts for transplantation.

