Exploratory	
 • Calculated total autologous (donor) skin applied to Study Tx sites by Month 6 • Effect of total wound burden on rate of wound closure

Safety

Objectives	Outcome Assessments
Evaluate the safety of SOMA Tx	
 • Incidence of treatment-emergent AEs (TEAEs) throughout study • Incidence of TEAEs related to each of the Study Txs • Incidence of wound infection-related events at Study Tx sites • Clinically significant changes in vital signs throughout study compared to Baseline • Clinically significant changes in laboratory values between Baseline and Day 28

	
• Clinically significant changes in panel reactive antibodies (PRA) and anti-BSA levels between Baseline and Month 3• Concomitant medication use
--	-----------------------------------------------------------------------------------------------------------------------------------------------------------------------------------------------------------

Outcome Measures:

Number of treatment sites with complete wound closure without additional autografting at Month 2.

Number of subjects with durable wound closure of the study treatment sites without additional autografting at Month 12.

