2.2.4 Safety Objectives

The safety objective is to evaluate the safety of SOMA treatment. At the same time, the safety of control treatment, i.e., autograft, site will also be displayed for reference, where applicable. The safety measurements are as follows:

- Incidence of treatment-emergent AEs (TEAEs) throughout study.
- Incidence of TEAEs related to each of the Study Tx's.
- Incidence of wound infection-related events at Study Tx sites.
- Clinically significant changes in vital signs throughout study compared to Baseline.
- Clinically significant changes in laboratory values between Baseline and Day 28.
- Clinically significant changes in panel reactive antibodies (PRA) and anti-bovine serum albumin (BSA) levels between Baseline and Month 3.
- Concomitant medication use.

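### SAP 3.8.4 plans no within-subject change output for anti-BSA, and reports HLA positivity only as separate visit percentages that cannot show new conversions

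*SAP*

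**What the plan says.** The endpoint has the same substance in both documents. Protocol 4 lists "Clinically significant changes in panel reactive antibodies (PRA) and anti-BSA levels between Baseline and Month 3", and SAP 2.2.4 repeats it: "Clinically significant changes in panel reactive antibodies (PRA) and anti-bovine serum albumin (BSA) levels between Baseline and Month 3". Blood is drawn for this purpose before StrataGraft placement and again at Month 3 (Protocol 9.2.6.2, SAP 3.8.4).

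SAP 3.8.4 is the only place where an analysis is specified. It plans four things:

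- Class-level positivity by visit: "The number and percentage of subjects that are HLA class I and II positive will be provided for Baseline (Day 1) and for Month 3".
- Allele-level positivity, as number and percentage at each visit.
- A three-level label for PRA parameters and anti-BSA IgG, which "will be categorized as normal, of non-clinical significance, and of clinical significance at Baseline and Month 3 by the central laboratory".
- A paired output for one of the two markers: "Shift tables indicating changes from Baseline to Month 3 for PRA results will be created using clinically significant categories by cohort".

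The list of departures from the protocol in SAP 2.2.7 does not mention anti-BSA. Protocol 10.3.3 (safety analyses) sets out no immunogenicity analysis.

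**The concern.** Two things look incomplete. First, anti-BSA IgG is sampled twice and labelled twice, but the sentence that turns labels into a Baseline-to-Month 3 comparison names PRA only. Followed literally, the plan collects the data for half of a stated safety endpoint and never compares a subject's two values. The omission is not declared. SAP 2.2.7 openly drops the wound-burden endpoint, so a reader would expect a dropped anti-BSA analysis to appear there too.

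Second, the natural question for HLA antibodies is how many subjects who were negative before treatment are positive afterwards. Two visit percentages do not answer it, because equal percentages can come from the same subjects or from different ones. SAP 3.1.1 imputes nothing here, so the two percentages can also rest on different subjects if a Month 3 sample is missing. For the low/normal/high shifts of CMP and CBC, SAP 3.8.2 restricts to subjects with both results. SAP 3.8.4 states no such restriction.

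At stake is the completeness of the immunogenicity report for an allogeneic product. PRA bears on antibody to human proteins, and anti-BSA on antibody to a component of the culture medium. Protocol 9.2.6.2 says that exposure may lead to anti-BSA antibodies.

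**Working it through.** The documents state no figure for this endpoint, so there is nothing to reproduce. The check sets the endpoint against the outputs and then asks what the visit percentages can and cannot identify.

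**Step 1. Outputs named in SAP 3.8.4, by marker**

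| Output | PRA / HLA | Anti-BSA IgG |
|---|---|---|
| Number and % positive at each visit | yes (class and allele) | not named |
| Clinical-significance label at each visit | yes | yes |
| Baseline-to-Month 3 shift of that label | yes | not named |
| Baseline-to-Month 3 cross-tabulation of positivity | no | no |
| Numeric change from Baseline | no | no |

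The third row corresponds to the endpoint as worded. It is filled for PRA and empty for anti-BSA.

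**Step 2. Does a general rule fill the gap?** SAP 3.1 makes frequency and percentage the default for discrete variables. Applied to the anti-BSA label, this gives counts per category at each visit. Those counts are unpaired and are not a change result. The change-from-baseline summaries in SAP 3.8.2 sit in the section on CMP and CBC.

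**Step 3. What two visit percentages say about conversion.** Let n subjects have both samples, b be positive at Baseline and m at Month 3, and let x be the number who go from negative to positive. Then m − x subjects are positive at both visits, and this must lie between 0 and b. Also, x cannot exceed the n − b who start negative. So

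max(0, m − b) ≤ x ≤ min(m, n − b).

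Input: n = 13, the number randomized (SAP 2.1), taking every pair as complete. The positive counts are assumptions, because the documents give none.

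| b | m | lowest x | highest x |
|---|---|---|---|
| 2 | 2 | max(0, 0) = 0 | min(2, 11) = 2 |
| 3 | 3 | max(0, 0) = 0 | min(3, 10) = 3 |
| 3 | 5 | max(0, 2) = 2 | min(5, 10) = 5 |
| 6 | 6 | max(0, 0) = 0 | min(6, 7) = 6 |

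In the second row both visits show 3/13 = 23%. The conversion proportion among Baseline negatives could be anywhere from 0/10 = 0% to 3/10 = 30%.

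**Step 4. Missing Month 3 sample.** Again with an assumed 3 of 13 positive at Baseline, suppose one of those 3 has no Month 3 sample and nobody changes status. The table would then read 3/13 = 23% and 2/12 = 17%, an apparent fall that reflects only the missing sample.

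**Step 5. Does the PRA shift table recover conversion?** Not necessarily. It pairs each subject's two clinical-significance labels, and SAP 3.8.4 gives no criteria linking those labels to positivity. A subject could become HLA-positive and keep the same label.

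**The case against.** The strongest reply is that the endpoint concerns clinically significant change, and that the PRA shift table is a paired, within-subject display of exactly that. This stands. A reader might infer that the PRA endpoint is not derived at all, but the documents do not support that. A rise in level that is not judged clinically significant lies outside the endpoint, so numeric change in PRA is useful supporting information and not a missing endpoint.

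A second reply is that leaving anti-BSA out of the shift-table sentence is probably a slip of a few words. The section heading names both markers, the preceding sentence labels both, and the table shells and programming specifications are separate documents that may include an anti-BSA table. This is fair, and it means nobody can say that anti-BSA will go unreported. It does not remove the gap in the SAP, which is the document that prespecifies the analysis.

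Two further inferences are tempting and should not be drawn:

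- Protocol 3.3 warns that subjects who mount an immune response to the allogeneic cells and later need a solid organ transplant "could experience a narrowing of the suitable donor pool". That risk bears on PRA. The documents do not connect it to anti-BSA, so it cannot be used to raise the importance of the anti-BSA gap.
- Clinical significance is assigned by the central laboratory here, but "at Baseline and Day 28 by the clinician" for CMP and CBC. This is not an inconsistency that needs correcting. The immunology assays are run centrally and CMP/CBC locally, and Protocol 9.2.4, which covers both, already has the investigator review laboratory reports and record clinically relevant changes.

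**Conclusion.** The point holds in two parts. As written, SAP 3.8.4 gives no within-subject change output for anti-BSA, which is one of the two markers in a stated safety endpoint; default summaries would give visit counts at most. For PRA the endpoint as worded is addressed, but the HLA class I and II positivity summaries cannot identify negative-to-positive conversion.

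No size can be put on either part from the documents. The range of 0 to 3 conversions among 10 Baseline negatives is an illustration that assumes 3 positives at each visit and 13 complete pairs. The finding concerns the SAP text only and assumes nothing about the unseen table shells, programming specifications or central laboratory manual. It affects the completeness of safety reporting and leaves the efficacy conclusions untouched. The correction is worth making because it is nearly free.

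**What to change.** In SAP 3.8.4:

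1. Extend the Baseline-to-Month 3 shift tables to cover anti-BSA IgG as well as PRA.
2. Add a paired Baseline-by-Month 3 negative/positive table for HLA class I and another for class II. Restrict both to subjects with both samples, and state the number converting among those negative at Baseline.
3. List both markers by subject at both visits, with numeric levels where the central laboratory reports them.

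The cost is a few lines of SAP text, a handful of small tables and one listing. No sampling is needed beyond the two draws already scheduled. The downside is that the paired tables lose any subject without a Month 3 sample, so the number of complete pairs should be shown. If the database is already locked, the same outputs can be added to the CSR and identified there as unplanned, which SAP 1 allows.

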4 AMENDMENTS TO THE SAP

This is the final SAP (version 1) based on the latest protocol Amendment 5 which was approved on 28 September 2023. The drafted SAP (version 0.1) was created on 26 Aug 2020.

5 PROGRAMMING SPECIFICATIONS AND CONSIDERATIONS

The corresponding programming specifications for variables for this SAP will be provided in a separate document.

6 TABLE, LISTING, AND FIGURE (TLF) SHELLS

The corresponding TL shells for this SAP will be provided in a separate document. Figures will not be provided for the abbreviated CSR.

Confidential and Proprietary

7 APPENDIX

None.

